For the study we will recruit participants from the community. Information needed to determine whether research participant meets eligibility requirements will be obtained during an initial phone-screen (see attached – using questions drawn from the Mini International Neuropsychiatric Interview (MINI)). If research participants meet the inclusion criteria based on the phone screening, they will be scheduled for an in-person or remote initial clinical assessment. Trained assessors will go through each criterion and document whether the research participant is eligible for the study using a standardized assessment checklist. If research participants meet the inclusion criteria based on the clinical assessment, they will be scheduled for an in-person or remote clinical intake. Research participants will be included if they meet the following criteria:

Individuals will be included if they:

1. Are 18 to 70 years old
2. Have experienced 12 or more loss of control episodes within the previous 3 months
3. Have a BMI above 18.5
4. Are located in the US and willing/able to participate in remote treatment
5. Are able to give consent

Individuals will be excluded from the study if they:

1. Are unable to fluently speak, write and read English
2. Are already receiving treatment for an eating disorder (e.g., research participants cannot be receiving concurrent eating disorder treatment from another provider)
3. Have a mental handicap or are currently experiencing severe psychopathology that would limit their ability to engage in study (e.g., suicidality, substance use disorder, active psychotic disorder, severe depression with suicidal intent)
4. Are purging and/or using laxatives 3 or more times per week and are not deemed safe for outpatient treatment by a primary care provider
5. Are unwilling to receive medical clearance and/or medical monitoring as requested by the study to ensure they are medically safe to participate
6. Are pregnant or planning to become pregnant within the next year
7. Are individuals who are not yet adults (infants, children, teenagers)
8. Are currently taking any of these medications: Haldol, Loxitane, Mellaril, Moban, Navane, Prolixin, Serentil, Stelaxine, Trilafon, Thoraxine, Abilify, Clozaril, Geodon, Risperdal, Seroquel, Zyprexa
9. Are adults unable to consent

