Eating disorders are associated with suicidality and studies utilizing eating disorder samples have a plan to ensure the adequate assessment and treatment of suicidality. If study staff or clinicians become aware of a clinically significant increase in depression or the emergence of suicidal ideation or self-harm behavior, the participant will undergo a comprehensive assessment of suicide ideation, plan, and intent with [name] (a Licensed Clinical Psychologist), and the necessary precautions will be taken to ensure safety or medical attention as appropriate. If high acute risk for suicidal ideation is discovered, [name] will make a telephone connection to a crisis resource (i.e., 24-hour crisis lines at [contact]) while maintaining contact with the participant in order to make a direct transfer. In addition, [name] will also immediately connect these participants with mental health emergency for hospitalization. These participants will be removed from the study so their suicidal ideations can be fully addressed. If intermediate acute risk and low acute risk for suicidal ideation is discovered, [name] will provide participants with contact information for mental health care provider and will be instructed to use mental health resources in case of psychiatric emergency or suicidality (i.e., 24-hour crisis lines at [contact]) that occurs outside of standard business hours when [name] could not be reached. These participants will be allowed to continue their study participation. [name] will maintain contact

PROTOCOL TITLE: Using factorial design to examine efficacies of technology-based augmentations for improving treatment adherence and skills utilization in a self-help CBT program for binge eating.

Protocol Version Date: April 19, 2022

mental health provider to determine acuity of referral. This method for assessing and intervening on suicidal ideation or risk for serious self-harm is currently standard practice in the WELL clinic and has been used successfully in our other clinical trials for BN and BED.

Ensuring participants receive high-quality interventions.

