Participants will continue in their current medical treatment at time of enrollment. Medical status will be closely monitored throughout the intervention. Participants will be required to sign consent to contact their PCP throughout the study to ensure coordination in care. The PCP will be provided with a letter describing enrollment in the study. Participants will be informed that the research team will inform the PCP if there is a change in symptom status such as notable weight loss, increase in restrictive eating behavior or increase in purging behavior that may require additional medical management. Concurrent psychotherapy for eating pathology will not be permitted during the study as this could confound data. Pharmacological management will be permitted for psychiatric co-morbidities. Any prescribed medications or dosage changes will be carefully tracked through the study.

Assessment Procedure. Assessments will occur at at baseline, mid-treatment, post-treatment, and at 3-month follow-up. In order to maximize assessment completion, we

PROTOCOL TITLE: Using factorial design to examine efficacies of technology-based augmentations for improving treatment adherence and skills utilization in a self-help CBT program for binge eating.

Protocol Version Date: April 19, 2022

will increase compensation across assessments (\$20, \$30, \$50 and \$75). At the beginning of the assessment at the baseline, the assessor will review the IRB approved Consent Form with the prospective participant. Of note, none of the assessments within the proposed study requires prospective participants to provide their signatures except for the Consent Form. Assessments will be conducted by Independent Evaluators (IEs), IEs will be trained until they reach 100% agreement on diagnosis and acceptable reliability (>.80) on EDE scoring. Assessments will be audio recorded for review. Twenty randomly selected tapes will be reviewed to compute reliability statistics. All measures listed below have acceptable psychometric properties.

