safeguard participants' data and privacy, in treatment conditions when JITAs are turned ON, following steps will be taken. 1) Intervention messages will only be accessible via smartphone app which will be password protected, 2) Intervention messages will be nondescript and will not include participant's PHI including information pertaining to mental health diagnosis or treatment, and 3) Push notifications will not contain any sensitive information.

13) Provisions to Monitor the Data to Ensure the Safety of Subjects

Participants will continue in their current medical treatment at the time of enrollment. Medical status will be closely monitored throughout the intervention. Participants will be required to sign consent to contact their PCP throughout the study to ensure coordination in care. The PCP will be provided with a letter describing enrollment in the study. Participants will be informed that their study staff will inform the PCP if there is a change in symptom status such as notable weight loss, increase in restrictive eating behavior, or increase in purging behavior that may require additional medical management. If the study team becomes aware of worsening levels of disordered eating symptoms that could pose an acute danger to the research participant's health, we will work with them to get touch with their primary care physician and encourage additional medical monitoring to ensure they are safe and stable enough to be receiving outpatient treatment based on their primary care physician's discretion. If they do not have access to a primary care physician, we will help them locate one. We will also provide referrals for treatment. Concurrent psychotherapy will not be permitted during the study as this could confound data. Pharmacological management will be permitted for psychiatric comorbidities. Any prescribed medications or dosage changes will be carefully tracked through the study.

14) Withdrawal of Subjects

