Research participants will be withdrawn from the study if they no longer meet the study criteria and/or they experience any acute life-threatening incident (precipitous drop in weight, change in electrolyte balance, etc.), hospitalization, suicidal or homicidal ideation, or serious self-harm behavior, failure to comply with study procedures. Condition of pregnancy will be assessed during the baseline, mid-treatment, post-treatment, and 3 month follow-up. If the research participant finds out that they are pregnant or plan on becoming pregnant within the next year during their time in the study, they must notify the project coordinator immediately. They will no longer meet study criteria and will be withdrawn from the study immediately. If termination is found necessary, the research participant will be contacted by the project coordinator immediately and the necessary precautions will be taken to ensure safety or medical attention as appropriate. The research participant will then be provided with referrals to other programs or studies if applicable and the data will be destroyed/banned from use. If, at any time, the treating physician determines that the health of the research participant precludes continuation of outpatient treatment, a meeting will be scheduled with the treating physician, research participant, and study staff to assist in locating referrals for appropriate levels of care. If a higher level of care is sought, research participants will be removed from the trial. Research participants are given the option to be added to our study database to be contacted for other studies they

PROTOCOL TITLE: Using factorial design to examine efficacies of technology-based augmentations for improving treatment adherence and skills utilization in a self-help CBT program for binge eating.

Protocol Version Date: April 19, 2022

might be eligible for at the WELL Center in the future. If they choose not to be entered into the database, all their information will be destroyed.

15) Risk to Subjects

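### Protocol section 13 bars all concurrent psychotherapy, section 10 bars it only for eating pathology, and screening asks only about eating-disorder treatment

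*Protocol*

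**What the plan says.** All of the relevant text is in the Protocol.

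- **Section 5, exclusion 2** reads "Are already receiving treatment for an eating disorder", with the illustration that "research participants cannot be receiving concurrent eating disorder treatment from another provider". Psychotherapy for any other condition is not mentioned.
- **Section 10**, in the paragraph on medical care just before the assessment procedure, states: "Concurrent psychotherapy for eating pathology will not be permitted during the study as this could confound data".
- **Section 13**, on safety monitoring, states: "Concurrent psychotherapy will not be permitted during the study as this could confound data".
- **Section 14** states: "Research participants will be withdrawn from the study if they no longer meet the study criteria". The same sentence also makes non-compliance with procedures a ground for withdrawal. The section goes on to say that, where termination is found necessary, the participant's data are destroyed or barred from use.
- **Section 24** says that people who discontinue treatment will be encouraged to carry on with the paid assessments.

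On medication, section 10 says "Pharmacological management will be permitted for psychiatric co-morbidities", and section 13 says the same. Exclusion 8 in section 5 begins "Are currently taking any of these medications" and lists 16 drugs.

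No text says whether section 10 or section 13 governs concurrent psychotherapy.

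**The concern.** Sections 10 and 13 cover the same period and give the same reason, confounding, but set different limits. The screening criterion matches the narrower one. Staff working from section 5 and section 10 would enrol and keep a participant in therapy for a non-eating condition. Staff working from section 13 would treat that participant as in breach.

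The difference matters most after randomization. Seeking therapy is plausibly related to symptoms, so removals on this ground may be informative. The SAP plans likelihood-based methods and multiple imputation, with sensitivity analyses if missingness depends on the outcome. Those methods draw on whatever was observed before a person left. If section 14's data sentence is applied, that information is lost too, and the randomized person contributes nothing. A loss caused by ambiguous wording is better prevented than modelled.

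**Working it through.** There is no figure in the plan to reproduce. The check is to take test participants through each rule as written.

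| Test participant | Section 5, exclusion 2 (entry) | Section 10 (in study) | Section 13 (in study) |
|---|---|---|---|
| A. In psychotherapy for a non-eating condition | Not excluded | Not barred | Barred |
| B. In psychotherapy for the eating disorder | Excluded | Barred | Barred |
| C. Receiving eating-disorder treatment other than psychotherapy from another provider | Excluded | Not covered | Not covered |
| D. Starts psychotherapy for a non-eating condition after randomization | Entry criterion already met | Not barred | Barred |

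1. **Case A is the conflict.** The person need not fall under exclusion 3, which concerns psychopathology severe enough to limit engagement. Therapy for a milder comorbidity passes every entry criterion, and the breach arises only from section 13.
2. **Case B shows no conflict.** All three places agree.
3. **Case C is a difference in scope.** An entry exclusion for any eating-disorder treatment and an in-study bar on psychotherapy can both be followed. Sections 5 and 10 do not contradict each other.
4. **Case D** has the same conflict as A, but no change to screening can prevent it. It needs an explicit in-study rule.
5. **Consequence for A and D.** Section 14 allows withdrawal for not complying with procedures, and its later sentence removes the data. Section 24 points the other way for people who merely stop treatment. The protocol does not say which handling applies to someone in breach of the psychotherapy rule.
6. **Record keeping.** Sections 10 and 13 both track prescribed drugs and dosage changes. No corresponding record of psychotherapy is described, and the assessment schedule has no item for it. As written, the trial could not report how many participants were in case A or D, or in which conditions.
7. **Medication.** Sections 10 and 13 agree with each other. The open question is whether exclusion 8, worded for current use at entry, is a continuing criterion under section 14. Section 14 does apply one entry criterion, pregnancy, after enrolment, but says nothing on drugs.

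**The case against.** The strongest reply is that this is a copying slip. The section 13 paragraph repeats the section 10 paragraph closely, and its psychotherapy sentence follows text about worsening eating symptoms and referral. Reading section 13 with section 10's qualifier is natural. It can also be said that section 10 does not expressly permit other psychotherapy, so obeying the stricter sentence satisfies both. The first argument is plausible, but the documents do not confirm it. The second does not help, because screening does not apply the stricter rule and would admit people who are in breach from the first day. It also remains true that no sentence attaches withdrawal to the psychotherapy bar by name. That step is an inference from the general non-compliance ground.

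A reader might infer more than the text supports in four ways.

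- **That three places contradict one another.** They do not. The conflict is section 13 against section 10, with section 5 permitting only by silence.
- **That the suicide-risk plan in section 10 sends people into therapy that section 13 forbids.** The plan gives participants at low or intermediate risk provider contacts and crisis lines and adds "These participants will be allowed to continue their study participation". It does not say that psychotherapy will start. Separately, section 14 lists suicidal ideation as a withdrawal ground. Those passages must be reconciled in any case, but that does not depend on the psychotherapy rule.
- **That a listed drug started mid-study is both permitted and a reason for withdrawal.** A general permission beside a specific exclusion list is ordinary drafting. The clash arises only if exclusion 8 continues after enrolment, which is unclear.
- **That the rule could exhaust the retention allowance.** The SAP's criterion is retention above 75%. Since 0.75 × 76 = 57, at least 58 must be retained and 76 − 58 = 18 may be lost. Setting psychotherapy users against those 18 needs a prevalence that the documents do not give, and needs every affected person to be withdrawn.

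**Conclusion.** The inconsistency is real and is in the current protocol text. A participant in psychotherapy for a non-eating condition is acceptable under sections 5 and 10 and in breach under section 13. Section 14 leaves open withdrawal and loss of that person's data.

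The size cannot be estimated, because the documents give neither the share of participants in other psychotherapy nor the likelihood that a breach would lead to withdrawal. All that can be said is that each removal costs 1/76, or 1.3%, of the randomized sample. The conclusion rests on reading section 13 literally and on section 14's non-compliance ground reaching this breach. If section 13 merely lost a qualifier, the correction is one phrase, but the gaps on recording therapy and keeping data remain. The medication question is secondary and is an ambiguity. Which treatments to allow is for the sponsor; this point takes no position on it.

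**What to change.** 1. Reconcile the psychotherapy sentences in sections 10 and 13 into one rule, in identical words. The sponsor chooses the scope.
2. Make exclusion 2 in section 5 match that rule, so that nobody is enrolled under one limit and judged under another.
3. State how the rule applies to psychotherapy that starts after randomization, since screening cannot catch it.
4. Record the start date of any concurrent psychotherapy at each assessment, alongside the medication tracking already planned.
5. Reconcile the data-destruction sentence in section 14 with the continued-assessment sentence in section 24, so that randomized participants' data are kept and assessments continue.
6. As a secondary item, state whether exclusion 8 continues to apply after enrolment, given the permission in sections 10 and 13 for drug treatment of psychiatric comorbidity.

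The cost is a short wording amendment and one extra dated field. If the broad bar is kept, screen failures will rise. If the narrow bar is kept, some participants will have other psychotherapy in the background. With 76 people in four conditions, randomization does not guarantee that this is balanced, and therapy begun later may depend on condition, so the dated record is needed under either choice.

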PROTOCOL TITLE: Using factorial design to examine efficacies of technology-based augmentations for improving treatment adherence and skills utilization in a self-help CBT program for binge eating.

Protocol Version Date: April 19, 2022

algorithm-identified moments when participant could benefit from receiving an intervention for improving two key areas including 1) treatment adherence, and 2) skills utilization based on responses (or lack thereof) in self-help app. For example, JITAIs will be delivered during times when treatment adherence is low (e.g., when participant has missed tracking for several days in a row, when participant has not updated weekly goals on the self-help app). JITAIs may deliver an intervention educating about relationship between low adherence and poor outcomes and suggest strategies to make progress in the following days. JITAIs will also be delivered during times of machine learning algorithm-identified moments when treatment skills use may be beneficial (e.g., participant reports an urge to binge, report skipping a meal/snack). In this case JITAIs may deliver interventions encouraging use of specific skills with brief instruction for skills implementation. For example, if a patient reports having an urge to engage in binge eating, the machine learning algorithm will identify that this patient is at risk for a binge episode in the near future. As a consequence, the JITAIs system will send automated interventions to coach a person on using urge management skills to prevent binge eating occurrence.

When JITAIs are turned OFF, participants will not receive interventions in real-time on the base self-help app.

When Advanced DDS with Coaches and JITAIs are both ON, while participants will continue to receive machine learning informed interventions, coaches will also have the ability to create and send interventions via the digital data portal to provide additional support. For instance, coaches will have the ability to write an intervention and schedule its delivery at a time when they believe participant will be at high risk for ED symptoms.

Consent procedures.

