- ***Eating Disorder Diagnosis***. This measure will be used to determine a research participant's eating disorder diagnosis based on the presence, frequency, and duration of pathological behavioral symptoms a research participant endorses at the assessment point.
- ***Feedback Questionnaire***. This measure will be used to assess research participant's overall enjoyment and perceptions of the treatment and assessments. The measure

PROTOCOL TITLE: Using factorial design to examine efficacies of technology-based augmentations for improving treatment adherence and skills utilization in a self-help CBT program for binge eating.

Protocol Version Date: April 19, 2022

will be conducted as an interview at mid-treatment (after 6 weeks of treatment) and post-treatment (after 12 weeks of treatment).

Self Report Measures

- ***Demographics Questionnaire (DQ)***. The Demographics Questionnaire will assess information such as age, sex, gender, sexual orientation, ethnicity, and SES.
- ***Dieting and Weight History Questionnaire (DWHQ)***. The DWHQ evaluates weight suppression, weight history, current and previous dieting history.
- ***Beck Depression Inventory-II (BDI-II)***. The BDI-II measures depression symptomatology over the past 2 weeks.
- ***Quality of Life Inventory (QOLI)***. The Quality-of-Life Questionnaire assesses quality of life across several life domains
- ***Short Positive and Negative Affect Scale (PANAS)***. The PANAS assesses positive and negative affect over a specified period of time.

Other measures

- ***Treatment adherence*** will be indicated by number of completed modules within 12 weeks of treatment, number of pages visited, number of worksheets completed, and goals setting each week using the app and self-monitoring compliance (i.e., number of days when self-monitoring was completed).

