Participants will receive compensation for their participation after each assessment point through QuickPay, a remote-payment electronic system at Drexel, which is administered by JPMorgan Chase Bank. This system allows us to compensate participants in the study through a secure electronic payment system (ACH) that is used by most major banks. This system securely sends direct payments from an account associated with this study to the participant's account, immediately upon study completion. The use of this system as a payment option allows for remote payment and helps us protect the privacy and safety of the participants and the research staff.

To use this form of payment, the participant number ID and your email and phone number will be provided to JPMorgan Chase Bank. Participants will receive an invitation to receive payment either as an email or a text message. Once you accept the invitation the funds will be disposed to your account by the next business day. Drexel University and the researcher team do not have any access to your account information, and they are not directly involved in the disbursement of the funds. If participants cannot or do not want to receive a direct, electronic payment through this system, they have the option of receiving a check from Drexel University. Alternatively, if participants do not want a check, we can send them an electronic Amazon gift card to their provided email.

Research participants who discontinue their participation in treatment will be encouraged to continue to participate in assessments for compensation. In order to facilitate completion of assessments and increase quality of data, all the assessments will be completed electronically and remotely. This will be via the secure on-line data collection site "REDCap". All data will be downloaded and stored in password protected files on Drexel-owned computers.

PROTOCOL TITLE: Using factorial design to examine efficacies of technology-based augmentations for improving treatment adherence and skills utilization in a self-help CBT program for binge eating.

Protocol Version Date: April 19, 2022

25) Number of Subjects

The current study is seeking to recruit 76 subjects to complete the treatment program. We plan to screen 150 subjects over the phone and conduct baseline assessments until 76 eligible participants are enrolled in the study.

26) Confidentiality

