## STATISTICAL DESIGN AND POWER

Descriptive statistics and exploratory graphing for all variables at all time points will be examined. We will compare baseline characteristics between treatment conditions using ANOVA for continuous variables and a chi-square test for categorical variables. Baseline variables that differ by treatment condition will be considered for use as covariates in the analyses described below. Patterns of missing data will be examined. Likelihood-based estimation methods and multiple imputation models will be used to handle missing data. If the missingness mechanism is related to the missing outcome itself, we will use sensitivity analyses to explore how robust our findings are with respect to a range of assumptions regarding missing data.

Primary Aim 1. To test target engagement of each intervention factor, we will model the pattern of change in treatment adherence and skills utilization separately over time using multilevel models (PROC MIXED in SAS). The first level will model individual participant's treatment adherence (or skills utilization) over time with baseline as time 0. At the second level, the individual intercept and slope will be entered as outcomes with each intervention factor as a predictor. We will examine each of the two intervention factors separately. The cross-level interaction between time and the intervention factor will be used to determine the effect of the intervention component on the pattern of change in the treatment targets.

Primary Aim 2. To assess feasibility and acceptability (primary aim 2), we will assess feasibility estimate (a) recruitment success (n=76) and (b) retention (>75% through all assessments), and (c) satisfaction via Likert ( $\geq$ "high") and coded interview ratings utilized in our team's previous clinical trials and other studies.

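### An undefined non-compliance withdrawal rule, combined with destruction of data, can delete randomized participants because of their value on a Primary Aim 1 outcome

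*Protocol*

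**What the plan says.** Section 14 of the protocol (Withdrawal of Subjects) is mandatory in form. Its grounds run from loss of eligibility and acute medical events to "hospitalization, suicidal or homicidal ideation, or serious self-harm behavior, failure to comply with study procedures". It does not say which procedures count, how much non-compliance is enough, or who decides. Once termination is found necessary, "the data will be destroyed/banned from use". The section's closing sentence adds that all information is destroyed for those who decline to join the centre's contact database.

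Section 10 (Other measures) defines treatment adherence by "number of completed modules within 12 weeks of treatment, number of pages visited, number of worksheets completed", together with weekly goal setting and days of self-monitoring. The SAP makes this a Primary Aim 1 outcome: "we will model the pattern of change in treatment adherence and skills utilization separately over time using multilevel models". Aim 4 then uses adherence as a mediator.

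Elsewhere low adherence is something to support, measure or follow up. Section 10 says that "JITAIs will be delivered during times when treatment adherence is low" and lists treatment attrition as a feasibility result, separately from study retention. Section 24 says: "Research participants who discontinue their participation in treatment will be encouraged to continue to participate in assessments for compensation".

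**The concern.** A participant who stops opening the app has a valid, very low adherence value. If that behaviour also counts as "failure to comply with study procedures", the same person must be withdrawn and the data lost. Selection then acts after randomization and on the outcome itself.

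Four things are at stake:

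- **Aim 1.** The ON versus OFF contrast on adherence is biased.
- **Aim 4.** The adherence range needed to relate adherence to binge eating is cut at its low end.
- **Aim 2.** Attrition and retention (target above 75%) come to depend partly on how staff read an undefined phrase.
- **Missing data.** The SAP's likelihood methods, multiple imputation and sensitivity analyses cannot use values that have been destroyed or banned, although the app log would have shown them.

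**Working it through.** **Inputs.** From the SAP (Power Analysis): d = 0.78 for adherence, N = 76, alpha 0.05, three assessment points, and a ratio of level-1 coefficient variability to residual variability of one. Assumed: a two-sided test, equal allocation (38 ON and 38 OFF per factor), a normal outcome, and no effect of the other factor. The share withdrawn for non-compliance is not in the documents, so 5% to 25% is used as a range. The SAP's 15% is an attrition allowance stated for binge eating frequency; here it is only one point in that range.

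**Step 1: reproduce the plan's figure.** For a linear-change model of the kind the SAP cites, λ = N·d² / [4(1 + V)] with V = 12/(M³ − M), referred to a non-central F on 1 and N − 2 degrees of freedom.

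- Adherence: M = 3, V = 12/24 = 0.5, λ = 76 × 0.6084 / 6 = 7.71, power 78.2%. The SAP states 80%.
- Binge frequency: N = 64, M = 4, V = 12/60 = 0.2, λ = 64 × 0.6084 / 4.8 = 8.11, power 80.1%.
- EDE global: N = 78, d = 0.70, M = 4, λ = 78 × 0.49 / 4.8 = 7.96, power 79.6%.

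The formula tracks the SAP closely enough to use for comparison.

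**Step 2: delete the lowest adherers with one common cut-off.** Let OFF be N(0, 1) and ON be N(0.78, 1). The cut-off c solves ½Φ(c) + ½Φ(c − 0.78) = p. The retained mean at level μ is μ + φ(a)/[1 − Φ(a)], with a = c − μ.

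For p = 15%:

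- c ≈ −0.73, so 23.4% of OFF and 6.6% of ON are removed.
- Retained means are about 0.40 and 0.92, a difference of 0.517.
- The pooled retained SD is about 0.82, so d = 0.517/0.82 ≈ 0.63.
- Retained N is 29.1 + 35.5 = 64.6, λ = 64.6 × 0.631² / 6 = 4.29, and power is 53%.

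**Step 3: check by simulation.** A three-point slope model was simulated with withdrawal triggered by a low mid-treatment value and all data of withdrawn participants deleted.

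| Withdrawn | OFF / ON removed | d | Power, selective loss | Power, random loss | Simulated slope difference | Simulated power |
|---|---|---|---|---|---|---|
| 0% | – | 0.78 | 78% | 78% | 0.78 | 79% |
| 5% | 8.4% / 1.6% | 0.72 | 69% | 76% | 0.72 | 72% |
| 10% | 16.1% / 3.9% | 0.67 | 60% | 74% | 0.67 | 65% |
| 15% | 23.4% / 6.6% | 0.63 | 53% | 71% | 0.65 | 60% |
| 25% | 36.8% / 13.2% | 0.57 | 41% | 66% | 0.60 | 50% |

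Random loss of the same size costs much less, so most of the damage comes from selection. The simulated losses are smaller at each level but go the same way. With no true effect and equal detection, the simulated rejection rate stays near 5%.

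**Step 4: relax equal detection.** Section 10 gives coaches the adherence portal only when Advanced DDS is ON. Keep the 15% cut-off and remove every ON participant below it, but only a fraction of those below it in OFF:

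| Fraction of OFF non-compliers noticed | d |
|---|---|
| all | 0.63 |
| half | 0.83 |
| a quarter | 0.90 |
| none | 0.97 |

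Between all and half the sign of the bias changes, and the effect is then overstated. This route applies directly to the DDS comparison. With equal allocation, coach visibility is balanced across the two JITAI levels.

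**The case against.** The best defence is that the rule was never meant for low app use. Where the Consent Process section (Section 30) gives an example of new study procedures, the example is assessment measures. The protocol's explicit conditions for staying in the study are medical clearance and monitoring, remote assessment, and no concurrent psychotherapy for eating pathology. The phrase closes a list made up mostly of safety events. On this narrow reading low adherers are kept, and Section 24 does not contradict Section 14, because leaving treatment and being removed from the study are different things. This stands as a possible reading. But the text does not adopt it, and a mandatory rule tied to data destruction should not depend on which reading staff choose.

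A reader might go further and infer that the rule removes people mostly from the OFF levels and so hides the effect. The documents do not support that. It needs a true effect and equal detection, and Step 4 shows the bias can reverse. Nor is adherence the sole primary outcome: Aim 1 pairs it with skills utilization, and the SAP also uses the term primary outcomes under the efficacy and mediation aims. Finally, the deletion figures hold only if withdrawn participants' data really are removed. If data up to withdrawal were kept, likelihood methods would use those low values and the loss would be smaller. Section 14 as written says they are not kept.

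**Conclusion.** The concern holds in a limited form. Section 14 contains an undefined, mandatory ground for withdrawal that can be read to cover a Primary Aim 1 outcome. Its data-destruction sentence turns withdrawal on that ground into outcome-dependent deletion after randomization. It also fits poorly with how Sections 10 and 24 treat low adherence and discontinuation.

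The direction of the bias is unknown. Under the stated assumptions with equal detection, d falls from 0.78 to between about 0.72 and 0.57, and SAP-model power from 78% to between about 69% and 41%. Under unequal detection at the 15% cut-off, d can rise to between 0.83 and 0.97. These are illustrations over an assumed 5% to 25% withdrawn, not forecasts. The matter should be settled before anyone is withdrawn on this ground, because destroyed data cannot be recovered and a bias of unknown sign cannot be corrected afterwards.

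**What to change.** 1. **Reconcile the protocol and SAP.** Bring Section 14 into line with Section 10 (JITAI triggers, feasibility measures), Section 24 and the SAP's Aims 1 and 2. Low use of the app, modules or self-monitoring should be handled as outcome data, not as non-compliance that leads to removal from the study and its analysis. Define what non-compliance does cover.
2. **Replace the data-destruction sentence for this ground.** State that data collected up to withdrawal stay in the analysis of all randomized participants, subject to consent. Align the closing sentence of Section 14 with this.
3. **Add an SAP rule for adherence.** For participants who simply stop using the app, take adherence from the log through week 12, counting uncompleted modules and untracked days as zero. Handle participants removed for safety or pregnancy separately, with a sensitivity analysis, and do not score them as zero by default.

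The safety grounds in Section 14 are not touched.

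The cost is a few sentences in each document and a little more analysis; the logs and assessments already exist. Each participant kept after baseline costs at most $30 + $50 + $75 = $155 in assessment payments. If 25% of 76 (19 people) were kept, that is at most 19 × $155 = $2,945.
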